9.4. Anticipated & Unanticipated (UADEs) Adverse Device Effects

9.4.1. Anticipated Adverse Events

Those **known** adverse events and surgical interventions related to the device or procedure are extrapolated from a population of 299 patients who underwent DBS for movement disorders (Medtronic® DBS™ Therapy for Parkinson's Disease and Essential Tremor CLINICAL SUMMARY, 2013):

- Abnormal behavior
- Abnormal dreams
- Activities of daily living impaired
- Adverse drug reaction
- Agitation
- Akinesia
- Anemia
- Anxiety
- Aortic stenosis
- Appendicitis perforated
- Arteriosclerosis
- Arthralgia
- Arthritis
- Asthenia
- Asthma
- Back pain
- Balance disorder
- Benign prostatic hyperplasia
- Biopsy bone
- Bladder catheter removal
- Blood pressure increased
- Bone Fractures
- Bone graft
- Bradykinesia
- Breast cancer
- Bronchitis
- Burns third degree
- Cardiac pacemaker insertion
- Cartilage injury
- Cellulitis
- Cerebral haematoma
- Cerebral haemorrhage
- Cerebrovascular accident
- Chest discomfort
- Chest pain
- Cholelithiasis
- Clostridium difficile colitis
- Clostridium difficile sepsis
- Cognitive disorder
- Complication of device removal
- Confusional state
- Constipation
- Convulsion
- Cough
- Debridement
- Decubitis ulcer
- Deep vein thrombosis
- Deep vein thrombosis postoperative
- Dehydration
- Delirium
- Delusion
- Delusional disorder, persecutory type
- Depression
- Depression suicidal
- Device electrical finding
- Device failure
- Device migration
- Diabetic ketoacidosis
- Diverticulitis
- Dizziness
- Drooling
- Drug hypersensitivity
- Drug toxicity
- Dysgraphia
- Dyskinesia
- Dysphagia
- Dyspnoea
- Dystonia
- Dysuria
- Erectile dysfunction
- Fall
- Fatigue
- Freezing phenomenon
- Gait disturbance
- Gastric polyps
- Gastroduodenitis
- Gastrointestinal disorder
- Gastrooesophageal reflux disease
- Glioma
- Grand mal convulsion
- Haematoma
- Haemoglobin decreased
- Haemorrhage intracranial
- Hallucination
- Head injury
- Headache
- Hiatus hernia
- Hip arthroplasty
- Homelessness
- Hyperhidrosis
- Hyperkalaemia
- Hypertension
- Hypoaesthesia
- Hypotension
- Hypovolaemia
- Hypoxia
- Implant site erosion
- Implant site infection
- Implant site reaction
- Incision site complication
- Incision site pain
- Inguinal hernia
- Insomnia
- Intestinal obstruction
- Intestinal perforation
- Intraventricular haemorrhage
- Labile blood pressure
- Labile hypertension
- Lethargy
- Localized infection
- Lumbar spinal stenosis
- Lung neoplasm malignant
- Major depression
- Malnutrition
- Mechanical complication of implant
- Mediastinal haemorrhage
- Medical device complication
- Medical device discomfort
- Medical observation
- Memory impairment
- Meniscus lesion
- Mental status changes

- Mental status changes postoperative
- Metabolic encephalopathy
- Mobility decreased
- Motor dysfunction
- Muscle rigidity
- Muscle spasms
- Musculo-skeletal pain
- Musculo-skeletal stiffness
- Musculoskeletal chest pain
- Nausea
- Neck pain
- Neuropathy peripheral
- Oedema peripheral
- Oesophageal spasm
- Oesophagitis
- Orchitis
- Orthostatic hypotension
- Osteoarthritis
- Pain
- Pain in extremity
- Paraesthesia
- Parkinson's disease
- Perseveration
- Pleuritic pain
- Pneumocephalus
- Pneumonia
- Pneumonia aspiration
- Pollakiuria
- Poor quality sleep
- Post-traumatic stress disorder
- Procedural complication
- Procedural pain
- Prostate cancer
- Prostate cancer metastatic
- Psychotic disorder
- Pyelonephritis
- Pyrexia
- Rapid eye movements sleep abnormal
- Rash
- Rectal haemorrhage
- Rectocele
- Restless legs syndrome
- Retinal detachment
- Reversible ischaemic neurological deficit
- Road traffic accident
- Rotator cuff repair
- Rotator cuff syndrome
- Scar pain
- Self-medication
- Sepsis
- Sexual dysfunction
- Sialoadenitis
- Small intestinal obstruction
- Somnolence
- Speech disorder
- Subdural haematoma
- Suicidal ideation
- Suicide attempt
- Syncope
- Syncope vasovagal
- Tooth abscess
- Transient ischaemic attack
- Treatment noncompliance
- Tremor
- Upper respiratory tract infection
- Urethral injury
- Urethral stenosis
- Urinary incontinence
- Urinary tract infection
- Urosepsis
- Viral infection
- Visual disturbance
- Vomiting
- Weight decreased
- Weight increased
- Wound dehiscence

The known or expected adverse effects that are attributable to stimulation are the following:

- Paresthesia
- Diplopia
- Dysarthria
- Dysequilibrium
- Paresis
- Dystonia
- Gait disorder
- Electrical shocking or jolting
- Headaches
- Pain, discomfort or local stress
- Attention deficit
- Dysphasia
- Insufficient therapeutic effect
- Ataxia
- Dyskinesia
- Sensory deficits
- Suicidal ideation
- Mania or hypomania
- Facial weakness
- Fatigue
- Loss of energy
- Numbness
- Other speech deficits
- Rebound symptom worsening with discontinuation of stimulation
- Transient heaviness in arm

- Changes in blood pressure or heart rate
- Nausea or vomiting
- Rapid or shallow breathing
- Anxiety
- Apathy
- Agitation
- Aggression
- Asthenia
- Balance disorder
- Akinesia
- Bradykinesia
- Chest discomfort
- Seizures
- Weight gain or weight loss
- Somnolence
- Tremor
- Undesired change in libido

9.4.2. Unanticipated adverse device effects (UADEs)

An unanticipated adverse device effect is “any serious adverse effect on health or safety or any life-threatening problem or death caused by, or associated with, a device, if that effect, problem, or death was not previously identified in nature, severity, or degree of incidence in the investigational plan or application (including a supplementary plan or application), or any other unanticipated serious problem associated with a device that relates to the rights, safety, or welfare of subjects” [21 CFR 812.3(s)]. Unanticipated means the event is not listed in the labeling, or the frequency or severity is greater than that reported in the labeling.

9.5. Adverse Event Reporting

Since we do not know in advance what, if any, adverse effects deep brain stimulation may have in this patient population, we will record and code any adverse clinical event on the Adverse Event form, whether it is mild or severe, and regardless of whether it is likely to be stimulation related or not. The AE forms will subsequently be analyzed to empirically determine which AEs are likely to be due to or exacerbated by the stimulation. We have developed specific procedures for coding AEs and have developed guidelines for breaking the blind should this be viewed as necessary by the treating physician. These procedures and guidelines are described below:

Two types of AE’s be recorded:

- A new onset AE refers to the onset of an abnormality in a patient previously determined to have normal function in that area. This would include such things as the onset of spasticity in a patient who had normal tone previously, or the development of a tremor in someone who had active movement without a tremor before.
- A worsening AE involves either an increase in severity of some symptom or some deterioration of function or ability. This would include such things as worsening hypertonia in someone who already had hypertonia. This category should be used once an adverse event has already been recorded, to indicate subsequent worsening of that adverse event.

Note that many AEs are, by their nature, chronic events with waxing and waning courses (e.g., behavioral dyscontrol) while others are discrete single events (e.g., development of a DVT). Chronic patterns will be reported as AEs only if their pattern of occurrence changes (i.e., the episodes become more frequent or severe), and will be considered resolved when the pattern returns to the pre-treatment baseline. New onset AEs which may become chronic patterns (i.e., a first episode of aggression) will be identified as starting at the time of the first event. AEs which

have no clear date of resolution but require long-term treatment will be considered ongoing until that treatment is completed (e.g., DVT with anticoagulant prophylaxis, osteomyelitis with prolonged antibiotic treatment).

In addition to recording descriptive information about the AE on the form, AEs will be characterized as anticipated or unanticipated (based on the previously-established side effect profile), a severity rating (reflecting seriousness and impact on clinical status) will be assigned, and the probability that the AE was related to the study treatment will be estimated (based on the plausibility to the known clinical effects of neurostimulation, and knowledge of other clinical risk factors for the AE). We will also indicate whether treatment of the AE was required, whether the study treatment was changed as the result of the AE, the date the AE resolved and the outcome of the AE.

9.5.1. Reporting Serious Adverse Events

The Sponsor-Investigator will direct all study personnel to inform him as soon as possible (within 24 hours) of any serious adverse event. If necessary, study personnel may communicate by telephone or e-mail, and follow-up later with completed case report forms. The Sponsor-Investigator will conduct an evaluation of the event and if it is determined to be a UADE, it will be reported as described in the following section.

9.5.2. Reporting UADEs

If an event is determined by the Sponsor-Investigator to be a UADE, he will report the event to the FDA and the IRB within the required timeframe of 5 business days if death or life threatening, and 10 business days if other serious criteria are met.

9.5.3. Stopping Rules

If two of the six study participants experience either a serious UADE or an adverse device effect that the Sponsor-Investigator determines would present an unreasonable risk to other participants enrolled in the trial, the Sponsor-Investigator must terminate the clinical trial 5 days after making that determination and not later than 15 days after the Sponsor-Investigator first receive notice of the effect.

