8. EARLY WITHDRAWAL OR TERMINATION

Subjects will be informed that they may withdraw or be discontinued (early termination) from this study at any time. Further, they will be informed that the Investigator may withdraw them if they fail to comply with the study requirements or if the investigator feels it is in the best interest of the subject to discontinue their participation. The reason(s) for withdrawal or early termination will be documented on the appropriate page of the CRF. No further study assessments will be performed after the subject has withdrawn.

Subjects who consent to participate but do not receive the DBS device will not count towards the 6 patients limit for this study and new patients will be screened. No attempt will be made to replace subjects who are withdrawn or prematurely discontinue their study participation after the device has been implanted.

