10. CLINICAL OVERSIGHT COMMITTEE

It is the responsibility of the Sponsor-Investigator to oversee the safety of the study participants. This includes careful assessment and appropriate reporting of adverse events as noted above.

In addition, a Clinical Oversight Committee (COC) has been appointed to conduct ongoing reviews of the safety of the Study and make recommendations regarding changes to the risk/benefit of the Study, including recommendations to discontinue new patient enrollments or discontinue the Study. The COC will review all SAEs as they occur and will conduct routine reviews at least quarterly throughout the study.

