10.1. Medical Monitor

An Independent Medical Monitor has been designated for this study to regularly assess reports of unanticipated study-related events. Once per quarter the Medical Monitor will review reports of any study-related unanticipated adverse events. The Clinical Oversight Committee will convene an ad hoc meeting to review any report of an unanticipated adverse event that is both study-related and serious.

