13.5. Protocol Compliance

Strict adherence to the protocol is expected. However, there are times when this is not possible. Any failure to follow the protocol (i.e. a deviation) must be identified and recorded. Deviations from the protocol which: (1) increase subject risk or (2) impact on study endpoints, will be

considered protocol violations. Protocol deviations and violations will be tabularized in the data listings.

Substantive changes to the protocol will require written FDA and IRB approval prior to implementation, except when such departures are necessary to eliminate an immediate hazard(s) to subjects. The IRB may provide expedited review and approval for minor change(s) in ongoing studies that have the approval of the IRB.

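### The two-of-six count in Section 9.5.3 also covers a device effect already judged an unreasonable risk to others, so that judgement in one participant triggers no required step there

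*Combined protocol and SAP*

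**What the plan says.** Section 9.5.3 opens: "If two of the six study participants experience either a serious UADE or an adverse device effect that the Sponsor-Investigator determines" to pose an unreasonable risk to the other participants. If that condition is met, the Sponsor-Investigator must end the trial "5 days after making that determination and not later than 15 days after the Sponsor-Investigator first receive notice of the effect". No lesser action is described.

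Other sections bear on a single event:

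- Section 10: "It is the responsibility of the Sponsor-Investigator to oversee the safety of the study participants". It adds: "The COC will review all SAEs as they occur and will conduct routine reviews at least quarterly throughout the study". The COC may recommend halting enrolment or stopping the study.
- Section 10.1: the COC "will convene an ad hoc meeting to review any report of an unanticipated adverse event that is both study-related and serious". The Medical Monitor reviews study-related unanticipated events once a quarter.
- Section 9.5.2: a UADE goes to the FDA and IRB within 5 or 10 business days, depending on its gravity.
- Section 9.5.4: a death goes to the IRB within 24 or 72 hours, and to the FDA within 5 business days.
- Section 8: the investigator may withdraw a participant "if the investigator feels it is in the best interest of the subject to discontinue their participation".
- Section 13.5: departures from the protocol without prior approval are allowed when needed to remove an immediate hazard.

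**The concern.** The second limb of 9.5.3 is a judgement about the other participants: the device effect seen in one person is held to be an unacceptable risk for the rest. Requiring a second affected participant before that judgement has any consequence under the rule defeats its purpose. As worded, nobody has to decide and record what happens to the others once it is made.

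The person making the judgement is the sponsor, the investigator and the implanting surgeon (Section 12.1), which gives a dated, documented step particular value. What is at stake is the last implant, any staged second lead and, mainly, continued stimulation of people already implanted.

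**Working it through.** The plan states no event rate or operating characteristic for the two-of-six threshold, so there is no figure to reproduce. The check is a reading of the text with three small calculations.

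**1. Scope of the count.** The sentence has the form: if two of six experience either A or B, terminate. A is a serious UADE. B is a device effect determined to be an unreasonable risk to others. The count precedes the either/or and so applies to both.

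**2. What one event requires, given the unreasonable-risk determination.**

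| Event in one participant | Section 9.5.3 | Required elsewhere |
|---|---|---|
| Serious and unanticipated | Nothing | COC review as an SAE (10); ad hoc COC meeting if study-related (10.1); FDA and IRB report if a UADE (9.5.2) |
| Death | Nothing | COC review as an SAE (10); IRB and FDA reporting (9.5.4) |
| Serious but anticipated | Nothing | COC review as it occurs, no stated deadline (10) |
| Non-serious, unanticipated | Nothing | Quarterly Medical Monitor review if study-related (10.1); routine COC review (10) |
| Non-serious, anticipated | Nothing | Routine COC review, at least quarterly (10) |

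In every row the right-hand column would be the same without the determination. The third row is not remote: Section 9.4.1 lists cerebral haemorrhage, suicide attempt and seizures among anticipated effects. Such an event is a UADE only if it exceeds what was previously identified in nature, severity or incidence (9.4.2).

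**3. Longest gap between routine COC reviews.** 365.25 / 4 = 91.3, about 91 days. The treatment phase is 90 days (6.9). This bounds the wait for a routine review, not exposure, because earlier action is allowed.

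**4. The deadline clause.** It refers in the singular to one determination and one effect, which fits a one-event trigger better than a count of two. Let notice of the first event be day 0 and the second event day d. If the effect meant is the first, the limit is day 15 and has lapsed whenever d > 15. Stimulation first starts on day 66, 80 or 94 by cohort (6.8). Suppose, as an illustration, that a cohort 1 and a cohort 3 participant enrolled on the same day and had the same effect equally long after switch-on. Then d = 94 − 66 = 28, which is 28 − 15 = 13 days past the limit. If the effect meant is the second, the conflict disappears. The text does not say which.

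**5. Remaining reach.** Section 6.6.1 reports on the first 5 patients and plans for the final one, so 6 − 5 = 1 new implant at most. A staged second lead, allowed up to 60 days after the first, is a contingency. The rest is stimulation of implanted participants, 12 hours a day in the treatment phase.

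**The case against.** The strongest reply is that a single event is far from ignored. A reader might infer from 9.5.3 that one such event requires no study-level action anywhere in the protocol. The documents do not support that: the table shows COC review, ad hoc meetings, and FDA and IRB reporting for single serious events. This part of the objection stands and limits the point to what the determination itself triggers.

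The gap may also be narrower than the table suggests. The UADE definition in 9.4.2 ends with a broad clause on other unanticipated serious problems affecting participants' safety or welfare, and an unanticipated effect judged an unreasonable risk could be argued into it. That leaves anticipated effects as the clear cases.

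The Sponsor-Investigator has a general safety duty, may withdraw individuals, and may depart from the protocol "except when such departures are necessary to eliminate an immediate hazard(s) to subjects". Appendix 1 provides for reprogramming when adverse effects emerge. So the gap matters only if the determination is made and nothing follows. That is fair, but the first three are a general duty or options, reprogramming concerns the affected participant, and none is tied to the determination.

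The singular wording could also describe one judgement made after two participants are affected. That reading is possible, and it is a reason to clarify the text.

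Finally, Section 13.1 commits the study to 21 CFR 812. Its content is not reproduced, so nothing is claimed here about what it requires or whether 9.5.3 conflicts with it.

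**Conclusion.** The point holds in limited form. Under 9.5.3 as worded, a determination of unreasonable risk to others in one participant triggers no required step in that section, and the steps required elsewhere depend on seriousness or unexpectedness. The clearest gaps are a serious but anticipated effect (COC review without a deadline) and an anticipated, non-serious one (routine review only, up to about 91 days). The deadline clause is unclear on any count-of-two reading.

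This should be changed, but it is not a finding that participants are unprotected. It rests on the ordinary grammar of 9.5.3 and on the protocol text alone. Two further inferences should be resisted. The 91 days is not an amount of stimulation that the change would prevent, since anyone may act sooner and a review need not end in switching off. No probability of exactly one qualifying event is offered either, because the documents give no event rate.

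**What to change.** Separate the two limbs in 9.5.3:

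1. Any single determination that a device effect is an unreasonable risk to others triggers an ad hoc COC review within 5 days. The figure echoes the interval already in 9.5.3; another short period would serve.
2. No new implant or staged second lead proceeds until the COC recommendation is recorded and acted on.
3. For each implanted participant, a dated and reasoned decision is recorded to continue, reduce or switch off stimulation. It should weigh the rebound risk listed in 9.4.1 against the statement in 6.3 that withdrawal has no known safety issues. In the 21-day blinded phase, the blind-breaking guidelines mentioned in 9.5 apply.
4. Two of six remains the mandatory termination trigger for serious UADEs. State whether one unreasonable-risk determination confirmed on review also ends the trial, and which event starts the 5-day and 15-day clocks.

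A matching line in Section 10 can keep the COC's role advisory. Extending the same hold to every UADE, or lengthening the 60-day limit for a second lead by the length of the hold, is optional.

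The cost is a short amendment using a committee already appointed. Section 13.5 says "Substantive changes to the protocol will require written FDA and IRB approval prior to implementation", so approval time applies if the change is substantive. Other downsides are a possible short delay to the last implant or a second lead, possible rebound and up to 5 of 90 treatment days lost (5/90 = 5.6%) for a participant switched off during a 5-day review, and possible unblinding in the 21-day phase.

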9.5.4. Reporting Deaths and Suicides

For any death that occurs during the course of the study, the sponsor will notify the IRB within an expedited timeframe according to the following guidelines:

- Report the event within 24 hours when the death is unforeseen (unexpected) and indicates participants or others are at increased risk of harm.
- Report the event within 72 hours, for all other deaths, regardless of whether the death is related to study participation.

The sponsor will notify the FDA within 5 business days as noted above.

10. CLINICAL OVERSIGHT COMMITTEE

It is the responsibility of the Sponsor-Investigator to oversee the safety of the study participants. This includes careful assessment and appropriate reporting of adverse events as noted above.

In addition, a Clinical Oversight Committee (COC) has been appointed to conduct ongoing reviews of the safety of the Study and make recommendations regarding changes to the risk/benefit of the Study, including recommendations to discontinue new patient enrollments or discontinue the Study. The COC will review all SAEs as they occur and will conduct routine reviews at least quarterly throughout the study.

10.1. Medical Monitor

An Independent Medical Monitor has been designated for this study to regularly assess reports of unanticipated study-related events. Once per quarter the Medical Monitor will review reports of any study-related unanticipated adverse events. The Clinical Oversight Committee will convene an ad hoc meeting to review any report of an unanticipated adverse event that is both study-related and serious.

11. STATISTICAL PLAN

This is a feasibility study to inform the safety and efficacy of central thalamic-deep brain stimulation (CT-DBS) in the treatment of chronic cognitive impairment and residual disability caused by traumatic brain injury (TBI). The primary outcome measure used will be the Trail Making test and secondary outcome measures include measures of cognition (Ruff 2 & 7), physical symptoms (Rivermead Post-Concussion Symptom Questionnaire (RPQ)), psychological health (Patient Health Questionnaire-9 and Columbia Suicide Severity Rating Scale (C-SSRS)), quality of life (Traumatic Brain Injury Quality of Life (TBI-QoL subscales)), and measure of global function (Glasgow Outcome Scale-Extended (GOSE)). For the present study all baseline, procedural, and safety and effectiveness follow-up data will be summarized with appropriate descriptive statistics. For continuous variables we will summarize data by the mean, median, standard deviation, minimum and maximum. For non-continuous variables we will summarize by percentages and frequency distributions. We will tabulate data for all enrolled patients. Our statistical analysis will be limited due to the small sample size.

Exploratory statistical analyses of primary and secondary endpoints will be performed to identify potential relationships between the treatment and the outcome variables.

Adverse event data will also be reported and tabulated.

